#### 9.9.2 Pharmacodynamics

The final analysis will be preceded by a blind data review which consists of individual graphs per visit by time of all pharmacodynamic measurements by time. The graphs will be used to detect outliers and measurements unsuitable for analysis.

The PD parameters will be listed by treatment, subject, visit and time. Individual graphs by time will be generated.

All PD endpoints will be summarised (n, mean, SD, SEM, median, Min and Max values) by treatment and time, and will also be presented graphically as mean over time, with standard deviation as error bars.

Parameters will initially be analyzed without transformation, but if the data suggest otherwise, logtransformation may be applied. Log-transformed parameters will be back-transformed after analysis where the results may be interpreted as percentage change. To establish whether significant treatment effects can be detected with the parent-reported questionnaires (ABC) and physician-reported questionnaires (CGI-I), a paired T-test shall be conducted. For the ABC test, the difference between the baseline and end-of-treatment period subscale scores shall be calculated and used for statistical analysis.

To establish whether significant treatment effects can be detected on the NeuroCart® PD parameters (animal fluency, smooth pursuit eye movement, saccadic eye movements, adaptive tracking and finger tapping) and Withings Steel HR (physical activity, average heart rate, sleep duration, amount of times to wake up) parameters, each parameter will be analyzed with a mixed model analysis of covariance (ANCOVA) with treatment, time, and treatment by time as fixed factors and subject, subject by treatment and subject by time as random factors and the (average) baseline measurement as covariate.

The Kenward-Roger approximation will be used to estimate denominator degrees of freedom and model parameters will be estimated using the restricted maximum likelihood method.

The general treatment effect and specific contrasts will be reported with the estimated difference and the 95% confidence interval, the least square mean estimates and the p-value. Graphs of the Least Squares Means(LSM) estimates over time by treatment will be presented with 95% confidence intervals as error bars, as well as change from baseline LSM estimates.

The following contrasts will be calculated within the model:

- Treatment - Placebo

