## 1.4.4 Study design

**Rationale for part A (healthy volunteer study).** Clonazepam PK is variable due to variations in CYP3A4 activity. Although plasma sampling is not desirable in the ARID1B patient population, knowledge of PK is required to establish concentration-effect relationship and the development of PK/PD models. Therefore, we will first conduct a limited study in healthy volunteers where plasma PK and saliva PK are correlated.

De Gier et al show that there is a close correlation between salivary and plasma levels of diazepam [19]. In a similar study Hallstrom et al confirmed this correlation although the correlation coefficient was lower (0.81 versus 0.96) [20]. No plasma-saliva PK studies have been performed with clonazepam, but urine and saliva PK has been investigated in subjects undergoing withdrawal which show that clonazepam detection in saliva is extremely sensitive [21]. Considering the nature of this part of the study, we will only include healthy adult volunteers.

**Rationale for part B (cross-over study).** Since the ARID1B patient population is small, with significant variability between patients, but limited within patients as demonstrated by our study CHDR1828, and the disease itself is stable, a cross-over design has been selected for the current study. In order to establish the acute and chronic administration of clonazepam whilst taking into account the development of tolerance to some of the effects of benzodiazepines, there is a 3-week treatment period with detailed measurements on the first and last days. By combining measurement of biomarkers with clinically relevant endpoints (such as cognition and behaviour) we can establish clonazepam effect on both, and test whether responses to acute and chronic treatment correlate.

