## 3 STUDY DESIGN

## 3.1 Overall study design and plan

**Part A.** Open label study in healthy volunteers where pharmacokinetics of clonazepam will be measured in paired plasma and saliva samples. Detailed scheduling can be found in **Table 1**.

For part A, the total duration of the study for each subject will be up to 2 days divided as follows:

- Screening: Up to 28 days before dosing.
- Saliva PK study day: Day 1.

**Part B.** Two-way cross over, placebo-controlled randomized study. Each period will be 22 days and periods will be separated by approximately a three-week washout. Patients will be monitored in the clinic for 5 hours for safety, PK, and biomarker effects on day 1 and 22 in each period. Within those days, patients remain at home and fill in questionnaires, wear a smartwatch and perform home-based assessments. Detailed scheduling can be found in **Table 2**.

For part B, the total duration of the study for each subject is divided as follows:

- Screening: By telephone, up to 60 days before dosing;
- In clinic study days study period 1: Day 1 22 plus a down titration period of ±3 days;
- In clinic study days study period 2: Day 1 22 plus a down titration period of ±3 days;
- Trial@Home periods: Days 2-21
- Follow-up phone call: approximately 14 days after the last dose of each study period.

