## 7.3 Questionnaire assessments

The Dutch translation of the Aberrant Behaviour Checklist (ABC) will be used [24]. The ABC is a validated questionnaire used for patients with intellectual disability. It consists of 58 symptoms of which the severity of symptoms during the last 2 weeks is scored by parents on a scale of 0-3 (0 = no problem, 3 = the problem is very severe). Parents of ARID1B subjects will complete the questionnaire on day 1 and day 22 of the two treatment periods. Teachers or primary caregivers (in the case of institutionalized care) will complete the questionnaire at the earliest opportunity after day 1 and day 22.

The Clinician Global Impression Score (CGI) is a well-validated clinician-rated measure commonly used in drug studies because it allows the clinician to integrate all sources of information, including the parent/caregiver history, observations in the clinic, and reports from other sources, into a single rating of severity (CGI-S) and improvement (CGI-I) during treatment. The CGI-S will be assessed on day 1 of every treatment period.

For this assessment, the investigator considers all aspects of the subject's neurobehavioral function, including but not limited to internalizing problems, externalizing problems, and social engagement, and rates a scale employing a 7-point Likert scale. The CGI-I monitors improvement and is scored on a 7-point Likert scale: very much improved, much improved, minimally improved, no change, minimally worse, much worse, very much worse. The score will be determined via a semi-structured interview with parents on day 22 of both treatment periods. Furthermore, an additional score will be

determined via a semi-structured phone interview with teachers or primary caregivers at the earliest opportunity after day 22 of both treatment periods.

Conversations made for the CGI assessment will be recorded for review by an independent physician.

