### 9.4 Missing, unused and spurious data

All missing or incomplete safety and PD data, including dates and times, are treated as such. Missing test results or assessments will not be imputed. Missing PD data, indicated as 'M' in the data listing, will be estimated within the statistical mixed model using SAS PROC MIXED.

For graphical and summary purposes PD and safety values below the limit of quantification will be set to half  $(\frac{1}{2})$  of the limit of quantification. For analysis no undetermined values will be replaced.

If single data points for PK concentrations are missing, the AUC parameters will be derived by interpolating with regard to the two neighboring non-missing concentrations. For calculation of PK parameters, all PK concentration values below the quantification limit (BLQ) occurring prior to Cmax will be replaced by 0, except for embedded BLQ values (between two measurable time points) which will be treated as "missing". All BLQ values after Cmax will be treated as "missing". The handling of missing, unused and spurious data will be documented in the study report.

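### ABC is tested by a paired t-test on change from each period's own Day 1 score, which is less efficient than adjusting for those baselines and leaves out one-period patients

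*Protocol*

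**What the plan says.** Section 9.9.2 of the protocol sets the test for both questionnaires. For the parent-rated ABC and the "physician-reported questionnaires (CGI-I), a paired T-test shall be conducted". It then defines the ABC variable: "For the ABC test, the difference between the baseline and end-of-treatment period subscale scores shall be calculated and used for statistical analysis".

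Section 7.3 sets the schedule: "Parents of ARID1B subjects will complete the questionnaire on day 1 and day 22 of the two treatment periods". Each period therefore has its own baseline, and the paired test compares (Y1 − B1) with (Y2 − B2), where B is a Day 1 score and Y a Day 22 score.

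Three other places bear on this:
- Section 1.4.4 justifies the crossover by variability that is "limited within patients as demonstrated by our study CHDR1828, and the disease itself is stable".
- Section 9.4 states that "Missing PD data, indicated as 'M' in the data listing, will be estimated within the statistical mixed model using SAS PROC MIXED". Section 9.5.3 places a treated patient in the PD set on the strength of a single assessment after baseline. Section 6.3 lists ABC among the PD endpoints.
- Section 9.9.2 gives the NeuroCart and watch endpoints a mixed model with baseline as a covariate. ABC does not get one.

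**The concern.** In a crossover each patient is already his or her own control. Subtracting a separate baseline in each period brings two more measured scores, with their own error, into the contrast. If Day 1 says little about Day 22 beyond the patient's usual level, the subtraction adds noise and removes none. Adjusting for baseline lets the data set the weight; a change score fixes the weight at one.

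A paired t-test also needs both periods. A patient who leaves after period 1 belongs to the PD set but cannot enter the ABC test, and the mixed-model handling of missing PD data has no model to act in.

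ABC is one of the two scales named in the multiple-dose objective (section 2), and section 1.4.9 puts the national population at around 60 patients, so lost precision cannot easily be made up by recruiting more.

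**Working it through.** **Inputs.** Four parent ABC scores per patient (7.3). Twenty patients and 20% drop-out, so 20 × 0.8 = 16 completers (1.4.9). No ABC standard deviation, correlation or power is stated. Assumed: equal variance s² at the four visits, correlation rw between Day 1 and Day 22 of the same period, and rb between any two scores from different periods.

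**The plan's own figure.** The only power stated for a paired t-test endpoint is CGI-I: 80% for 1 point with SD 1.5. Reading 1.5 as the SD of the paired difference, two-sided 5%, the noncentral t gives 80.7% at n = 20, which reproduces it, and 70.3% at n = 16. There is no such figure for ABC to reproduce or contradict.

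**Variance of the paired contrast, per patient.**
- Day 22 scores only: 2s²(1 − rb).
- Change scores: each change has variance 2s²(1 − rw), and the two changes have covariance s²(rb − rb − rb + rb) = 0. Total: 4s²(1 − rw).
- Baseline-adjusted: 2s²(1 − rb)(1 − rho²), with rho = (rw − rb)/(1 − rb).

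Since 1 − rw = (1 − rb)(1 − rho), change/Day 22 = 2(1 − rho), and change/adjusted = 2(1 − rho)/(1 − rho²) = 2/(1 + rho). The second ratio exceeds 1 for every rho below 1.

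**Small-sample cost.** With 16 completers, eight per sequence, estimating one within-patient slope inflates the adjusted variance by about 1 + 1/(16 − 4) = 13/12 for a normal covariate. The expected ratio is then 12/13 of the large-sample one. The last two columns are simulated ratios (REML, n = 16) of change-score variance to that of a mixed model, with the baseline either split into patient mean and deviation or entered as the raw same-period score.

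| rw / rb | rho | change / Day 22 only | change / adjusted | × 12/13 | simulated, split | simulated, raw |
|---|---|---|---|---|---|---|
| 0.7 / 0.7 | 0 | 2.00 | 2.00 | 1.85 | 1.92 | 1.41 |
| 0.7 / 0.6 | 0.25 | 1.50 | 1.60 | 1.48 | 1.43 | 1.32 |
| 0.8 / 0.7 | 0.33 | 1.33 | 1.50 | 1.38 | 1.40 | 1.23 |
| 0.8 / 0.6 | 0.50 | 1.00 | 1.33 | 1.23 | 1.24 | 1.19 |

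The raw covariate does worse because one slope must serve both between-patient and within-patient differences. At 0.7/0.7 the fitted slope averages 0.64, although the best within-patient slope is 0. There the raw-covariate model has about 2.00/1.41 = 1.42 times the variance of simply comparing Day 22 scores.

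**Power, as illustration only.** Take an effect that Day 22 scores would detect with 80% power. The change score has 51% at rho = 0, 66% at 0.3, 80% at 0.5 and 88% at 0.6. Adjustment, before the small-sample cost, has 80%, 84%, 90% and 94%.

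**One-period patients.** With 16 complete and 4 one-period patients (treatment, period, random subject, known variances), including the four cuts the treatment variance by 5.9% at an intraclass correlation of 0.5, 2.4% at 0.8 and 1.2% at 0.9.

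**The case against.** The size depends on rho, which nobody knows here. The repeatability evidence from CHDR1828 concerns the test battery; in section 1.2 ABC appears only as a severity measure with which the tests were correlated. The stable-disease statement therefore does not establish rho = 0 for ABC. Day 1 and Day 22 of one period lie three weeks apart, while the two Day 22 visits lie about six weeks apart, so a positive rho is plausible. Against unadjusted Day 22 scores the penalty vanishes at rho = 0.5 and reverses above it. A period baseline also protects against shifts in level between periods. All of this stands, and it limits the claim to a comparison with baseline adjustment.

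On missing data, section 9.4 also rules out imputation, and its mixed-model sentence may be meant only for endpoints that have such a model. Section 9.5.3 defines a set and does not promise that every member enters every contrast. That softens a contradiction into a mismatch.

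A reader might also infer that clonazepam withdrawal contaminates the period-2 baseline, since "the severity of symptoms during the last 2 weeks is scored by parents" and "periods will be separated by approximately a three-week washout". No document reports a rebound on ABC, and a two-week recall leaves out roughly the first of those three weeks. What remains is narrower: a shift in that baseline, if there is one, enters a change score at full weight and an adjusted analysis only at the fitted slope.

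**Conclusion.** The point holds as one of efficiency and consistency. The prescribed ABC test is less efficient than a properly baseline-adjusted analysis for any rho below 1 in large samples: by a factor of 2.0 at rho = 0, falling to 1.33 at rho = 0.5. With 16 completers the factor is about 1.9 to 1.2 over the same range. It rests on equal visit variances, one common correlation across periods, and an assumed rho.

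A reader might infer that the plan doubles the ABC variance, or cuts its power from 80% to 51%. The documents do not support that as a finding: it is the limiting case rho = 0, and no ABC power is stated. Nor does leaving out up to 4 of 20 patients cost much information, since including them saves about 1 to 6% of variance at intraclass correlations of 0.5 to 0.9. The reason to include them is agreement with the plan's own analysis set and missing-data rule.

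The study has no primary endpoint (1.4.8), and no inflation of error rates is shown.

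**What to change.** In section 9.9.2, replace the ABC paired t-test with a mixed model for the Day 22 subscale score:
- treatment and period as fixed effects, subject as random effect;
- the Day 1 score entered as two covariates: the patient's mean of the available Day 1 scores, and the period's deviation from that mean (zero for a patient with only one);
- all patients in the PD set with a Day 22 score.

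Do not enter the raw same-period Day 1 score as the only baseline term, because its pooled slope gives away much of the gain.

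Report the period-2 Day 1 ABC by sequence, as a descriptive check on whether the baselines differ after the first treatment.

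The cost is wording only. All the scores are already collected, and section 10.6.2 classes statistical analyses other than those in the protocol as non-substantial changes.

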#### Sample Size Justification and statistical methodology

For part A, Linear and non-linear relationships between plasma and saliva concentrations will be explored. In the case of a nonlinear relationship, which could be expected due to delayed penetration in the salivary compartment, it is widely accepted that around 20 subjects are necessary to develop a reliable model. The predictive capability of the two regression equations will be compared to determine which method is superior.

For part B, the sample size is based on practical considerations (the total ARID1B population in the Netherlands) and based on the previous study (CHDR1828). We consider 20 patients to be a feasible amount of subjects to recruit, while obtaining sufficient power to detect clinically relevant treatment effects. To establish treatment effects the repeatedly measured cross-over PD endpoints will be analyzed by mixed model analyses of variance with treatment, period, time, and treatment by time as fixed effects, with subject, subject by treatment and subject by time as random effect, and with the (average) baseline value as covariate. The PK-PD relationship between clonazepam concentration and PD endpoints will be assessed by calculating the estimated plasma concentration using the derived formula in part A of the study.

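### Section 9.9.2 drops the period term that the synopsis puts in the crossover model, its paired t-tests also ignore period, and body sway is left out of the analysed NeuroCart parameters

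*Protocol*

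**What the plan says.** The protocol describes the mixed model for the crossover pharmacodynamic endpoints twice. The synopsis (Sample Size Justification and statistical methodology) has it "with treatment, period, time, and treatment by time as fixed effects, with subject, subject by treatment and subject by time as random effect". Section 9.9.2 has it "with treatment, time, and treatment by time as fixed factors and subject, subject by treatment and subject by time as random factors". The random terms are the same, and both carry an average baseline covariate; the only difference in the fixed part is period. Section 9.9.2 does not say whether "the (average) baseline measurement as covariate" is taken separately in each period or pooled over both.

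For the questionnaires, section 9.9.2 says that "a paired T-test shall be conducted". For the ABC, "the difference between the baseline and end-of-treatment period subscale scores shall be calculated and used for statistical analysis". The CGI-I enters as its end-of-period score.

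Section 9.9.2 lists the NeuroCart parameters to be modelled as "animal fluency, smooth pursuit eye movement, saccadic eye movements, adaptive tracking and finger tapping". Body sway is not among them. It is an endpoint in section 6.3, part of the test battery in Table 2, and has a minimum detectable effect of 301 mm in section 1.4.9.

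**The concern.** Two models are stated for one set of endpoints, so two different p-values per endpoint could each be called protocol-specified. That should be settled before the treatment code is opened.

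The choice has consequences. In a two-period crossover each patient has one treatment per period, so subject by treatment is the same grouping as subject by period. A period shift that is not modelled goes into the subject-by-treatment variance and widens the standard error of the treatment contrast. The paired t-test behaves in the same way: the shift adds to the difference in one sequence and subtracts in the other.

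A period effect is plausible for the performance tests. Screening is by telephone, so the first hands-on run of the battery in this study is Day 1 of period 1. The battery is then repeated through four clinic days, with three tests also done at home twice weekly. For the parent and clinician ratings a period effect through expectation is an inference; the protocol neither states nor excludes it.

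**Working it through.** **Inputs.** From section 1.4.9: CGI-I SD 1.5, target difference 1 point, stated power 80%, 20 subjects, 20% drop-out (16 completers). Assumptions: two-sided 5% test (9.9.2 reports 95% intervals); 1.5 is the SD of the within-patient difference, since the protocol does not say which SD it is; period effect π (period 2 minus period 1) from 0 to 1.5 points, since no value is given.

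**The plan's own figure.** A paired t-test with n = 20 has SE 1.5/√20 = 0.335 and noncentrality 1/0.335 = 2.98. On 19 df the power is 80.7%, so the stated 80% reproduces at 20 completers. With 16 completers the SE is 1.5/4 = 0.375 and the power is 70.3%. If 1.5 were the SD of a single score with no within-patient correlation, power at n = 20 would be 51.6%.

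**Model without period.** Let D be active minus placebo for one patient: D = τ + sπ + e, with s = +1 if active comes second and −1 if it comes first.

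- Bias of the mean of D = π × (n placebo-first − n active-first)/n. This is 0 at 10/10 or 8/8, 2/16 = one-eighth of π at 9/7, and 4/16 = one-quarter of π at 10/6. The sign depends on which sequence is larger.
- Expected variance of D with equal sequences = 1.5² + π² × n/(n−1). At n = 20 and π = 1: 2.25 + 20/19 = 3.30, an SD of 1.82. For π = 0.5 the SD is 1.59 and for π = 1.5 it is 2.15.

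**Model with period.** The treatment effect is the mean of the two sequence means of D, with SE (1.5/2) × √(1/n₁ + 1/n₂) on n − 2 df. At 10/10 this is 0.75 × √0.2 = 0.335, as before, and power is about 80% whatever π is.

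**Power for a true 1-point difference at 10/10** (simulation for the plain test):

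| π (points) | plain paired t | period-adjusted | type I error, plain |
|---|---|---|---|
| 0 | 81% | 80% | 5.0% |
| 0.5 | 77% | 80% | about 4% |
| 1.0 | 67% | 80% | 2.0% |
| 1.5 | 51% | 80% | 0.6% |

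At 8/8 and π = 1 the plain test has about 54% and the adjusted one 70%.

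**Unequal completers, π = 1.**

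| completers | bias against the drug | bias in favour of the drug | period-adjusted |
|---|---|---|---|
| 9/7 | 42% | 66% | 69% |
| 10/6 | 32% | 77% | 67% |

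**How likely is imbalance?** Section 5.5.1 does not state equal sequence sizes. If the trial starts at 10/10 and exactly 4 of 20 drop out at random, 8/8 has probability 45 × 45/4845 = 42%, 9/7 has 2 × 10 × 120/4845 = 50%, and 10/6 has 2 × 210/4845 = 9%.

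**Cost of the period term when π = 0** (plain and adjusted): 81% and 80% at 10/10, 70% and 69% at 9/7, 70% and 67% at 10/6.

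These figures are for the paired CGI-I comparison. The loss in the NeuroCart mixed model works in the same way but was not calculated.

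**The case against.** Most of the case on the other side stands.

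- A stable shift in level between periods cancels in the ABC change score if baseline is that period's Day 1 value. It should largely not enter the CGI-I, which already rates improvement within the period, and it is reduced in the NeuroCart model if the baseline covariate is period-specific. What remains is a period effect on the change itself.
- Practice effects concern the performance tests, whereas the power figures are for an interview-based rating. Table 2 also schedules an explanation of the tests and a pre-dose battery, so the first run is a baseline rather than an outcome.
- The size of the period effect is assumed. At 0.5 points the loss is only 3 to 4 percentage points of power.
- The paired t-tests do not contradict the synopsis, whose period model is for repeatedly measured endpoints. Replacing them gains efficiency; it does not correct an inconsistency.
- The study is exploratory, with no primary endpoint (1.4.8) and no multiplicity adjustment (9.9.3).

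None of this removes the disagreement between the synopsis and 9.9.2. An analysis plan could settle it, but it would have to depart from one of the two protocol statements.

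**Conclusion.** The point holds as a contradiction on the period term, a questionnaire analysis that ignores period, and one endpoint left out of the list of modelled parameters. The harm is mainly a loss of precision that depends on a period effect in the analysed quantity. On the assumptions used, CGI-I power at 10/10 falls by about 3 points for a period effect of 0.5, 13 points for 1.0 and about 30 points for 1.5.

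A reader might infer that every crossover comparison is biased. The documents do not support that: bias needs unequal completers by sequence, is at most one-quarter of the period effect in the splits examined, and can favour either treatment. Nor do false positives follow. The plain test's type I error did not rise above about 5% in any setting tried, and it fell well below 5% with equal sequences. The 32% power at 10/6 is one direction of a split that has about a 9% chance over both directions under random drop-out.

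The body sway omission is separate. Section 9.9.2 still summarises all PD endpoints descriptively, and the synopsis model would cover body sway, so this looks like an incomplete list; nothing in the protocol states a decision to drop it.

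This should be fixed, but in an exploratory study it is not critical.

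**What to change.** In section 9.9.2:

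1. Add period as a fixed effect to the mixed model so that it matches the synopsis, and say whether the baseline covariate is period-specific.
2. Replace the paired t-tests for CGI-I and ABC change by a period-adjusted crossover analysis, with treatment and period fixed and subject random. With complete pairs this is the sequence-stratified t-test used above.
3. Add body sway to the analysed NeuroCart parameters.

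The cost is wording and one degree of freedom, with about 0 to 3 points of power lost if there is no period effect. Section 10.6.2 classes a change of statistical analysis as non-substantial. The change should be made before unblinding.

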## 1.4.7 Treatment duration

Since clonazepam has been shown safe and effective in children, and treatment of ARID1B-related intellectual disability would require chronic administration, we have chosen a multiple-dose trial design. The choice for the duration of treatment is based partly on practical considerations and on data on the development of tolerance. It is known that tolerance to different effects of benzodiazepines develops on different time scales. Development of tolerance for sedative effects of benzodiazepines varies from 7 days to 2 weeks in most studies [22, 23], whilst development of tolerance to anti-epileptic

and anxiolytic effects needs much more time to develop. Therefore, we have chosen to treat patients for 3 weeks, to ensure we can establish the effects of clonazepam in absence of the potential sedative side-effects

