## 2 STUDY OBJECTIVES

- To test the hypothesis that clonazepam administration has acute beneficial effects compared to placebo on neurocognitive tests.
- To test the hypothesis that multiple-doses clonazepam has beneficial effects compared to placebo on behaviour and cognitive function in ARID1B patients as measured by the ABC, and CGI-I scale.
- Assess safety and tolerability of clonazepam in ARID1B patients.
- To assess the potential of at-home neurocognitive tests for the evaluation of treatment effects in children with neurodevelopmental disorders.
- To assess and compare the difference in predictive capability between linear and nonlinear (NONMEM) regression of the saliva:plasma relationship.

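### The single NeuroCart contrast in Protocol 9.9.2 carries no day, so read plainly it averages Day 1 with Day 22 and isolates neither the acute nor the chronic effect on these tests

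*Protocol*

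**What the plan says.** **Analysis (Protocol 9.9.2).** For NeuroCart and the smartwatch parameters, "each parameter will be analyzed with a mixed model analysis of covariance (ANCOVA) with treatment, time, and treatment by time as fixed factors". Subject, subject by treatment and subject by time are random, and baseline is a covariate. On reporting: "The general treatment effect and specific contrasts will be reported with the estimated difference and the 95% confidence interval", together with graphs of least-squares means over time by arm. Then: "The following contrasts will be calculated within the model". The list has one entry, "Treatment - Placebo". The synopsis version of the model adds period but no day or visit term, and enters the model "with the (average) baseline value as covariate".

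**Schedule (Table 2).** The NeuroCart battery is done on Day 1 and Day 22 of each period, at -1, 1, 3 and 5 h around dosing.

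**Questions asked.**
- The first objective in section 2 reads "To test the hypothesis that clonazepam administration has acute beneficial effects compared to placebo on neurocognitive tests".
- The second objective, on multiple dosing, is tied to ABC and CGI-I. Section 9.9.2 tests these by paired t-test.
- The title names both the acute and the chronic effect on cognitive tests.
- Section 1.4.4 explains that "there is a 3-week treatment period with detailed measurements on the first and last days", takes tolerance into account, and wants to know whether acute and chronic responses correlate.
- Section 1.4.7 sets three weeks of treatment "to ensure we can establish the effects of clonazepam in absence of the potential sedative side-effects", citing tolerance to sedation within 7 days to 2 weeks.

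**The concern.** The design measures two different conditions on purpose: the first low dose, when sedation is possible, and the third week, when tolerance to sedation is expected. The protocol's own rationale therefore allows the treatment effect to differ between the days, perhaps in sign. A treatment difference without a day, taken from a model without a day term, averages over that difference.

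The acute objective on neurocognitive tests is at stake, because NeuroCart is its only measure. So is the chronic cognitive effect that the title and 1.4.4 announce. An effect on one day only would be halved in the reported contrast, and an early impairment followed by a later benefit could appear as no effect.

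The baseline wording adds a conditional risk. Each clinic day has one pre-dose test. Within a period, the only second pre-dose value that could be averaged is the one on Day 22, taken after 21 days on treatment. If it entered the covariate, part of the chronic effect would be adjusted away.

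**Working it through.** **1. The plan's own power figure.** Section 1.4.9 states 80% power for a 1-point CGI-I difference with SD 1.5. A paired t-test with n = 20, SD of the within-subject difference 1.5 and two-sided alpha 0.05 (assumed from the 95% confidence intervals) has power 0.807, so the figure reproduces. The NeuroCart table in 1.4.9 gives detectable effects but no SDs, and does not say which day they refer to. It cannot be reproduced, so the rest is in standardised units.

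**2. Effect sized for one day.** With 20 subjects and 20% drop-out, 20 × 0.8 = 16 complete. A paired t-test with n = 16 has 80% power at d = 0.749 SDs of the treatment difference (noncentrality 0.749 × √16 = 3.00).

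**3. Pooled contrast.** Let w1 and w22 be the day weights, δ1 and δ22 the day effects in units of d, and ρ the correlation between the two day-specific treatment differences, with equal SDs.

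- Pooled effect = (w1·δ1 + w22·δ22)·d
- SE factor = √(w1² + w22² + 2ρ·w1·w22)
- Noncentrality = √16 × pooled effect / SE factor

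There are three post-dose times per day, so w1 = w22 = 0.5. For an effect on one day only, the pooled effect is 0.5 × 0.749 = 0.375:

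- ρ = 1: SE factor 1, noncentrality 1.50, power 0.289
- ρ = 0: SE factor 0.707, noncentrality 2.12, power 0.509
- ρ = 0.5 and 0.8 give 0.367 and 0.316

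| Day 1, Day 22 effect (× d) | Pooled effect (× d) | Power, ρ = 1 to ρ = 0 |
|---|---|---|
| 0, 1 or 1, 0 | 0.50 | 0.289 to 0.509 |
| -0.5, 1 | 0.25 | 0.108 to 0.168 |
| -1, 1 | 0 | 0.05 |
| 1, 1 | 1.00 | 0.800 to 0.977 |

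If the Day 22 pre-dose test also counts as an outcome, the weights become 3/7 and 4/7. Power is then 0.361 to 0.611 for a Day 22-only effect and 0.225 to 0.391 for a Day 1-only effect.

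**4. How different are the two days?** With the stated half-life of 20 to 40 h, and with 12-hourly intake and linear kinetics assumed, the accumulation ratio is 1/(1 - 2^(-12/t½)): 2.9 at 20 h and 5.3 at 40 h. The ratio of the Day 22 intake to the Day 1 intake depends on the reading:

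- The twice-daily list in 5.1, uncapped: 0.015/0.005 = 3
- The per-day text in 5.2, taken as two equal intakes: 0.0075/0.005 = 1.5
- At 70 kg under the list with the 0.5 mg cap: 0.5/0.35 = 1.43
- At 100 kg or more the cap makes both intakes 0.5 mg: 1

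Steady-state exposure on Day 22 is therefore between 1 × 2.9 = 2.9 times and 3 × 5.3 = about 16 times that after the first dose. A dose reduction for adverse events would lower it. Sections 5.1 and 5.2 contradict each other on this dose and must be reconciled. The point here does not depend on which reading applies.

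**The case against.** The strongest reply is that 9.9.2 never says the days are pooled. The entry may only name the arms to be compared. The same paragraph serves the smartwatch data, collected at home between the clinic days. Treatment by time is in the model, so day contrasts can be estimated if time indexes day and hour, and separate models per day are not excluded. Time points are often left to the SAP. The study is exploratory with no primary endpoint, and both days' data will be listed and summarised by visit or time.

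Part of this stands. Pooling is the plain reading of one model per parameter, no day term and an unqualified contrast, but it remains a reading. The protocol does, however, introduce a list of contrasts and give it one entry, and nowhere names a treatment difference by day. Graphs of arm means over time are not an estimated difference with a confidence interval. Exploratory status removes the multiplicity concern but does not say which effect the contrast estimates. Day contrasts chosen after unblinding would be the data-driven kind that 9.10 sets apart.

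Three stronger readings are not supported:
- A reader might infer that the trial tests neither of its two hypotheses. The multiple-dose hypothesis is written for ABC and CGI-I, whose paired t-tests the NeuroCart contrast cannot mask.
- A reader might infer that the Day 22 pre-dose value is part of the baseline. The text does not say what is averaged, so this is an ambiguity and not a shown error.
- A reader might take a fourfold exposure difference as the minimum. The cap brings it to about 2.9-fold at 100 kg or more with a 20 h half-life.

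**Conclusion.** The concern holds for NeuroCart. As written, the only listed contrast isolates neither the acute effect, which is a stated objective, nor the chronic cognitive effect, which the title and rationale seek. A one-day effect sized for 80% power on that day would have about 29% to 51% power in the pooled contrast, and equal and opposite effects would average to zero.

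These figures assume that the days are pooled with equal weights and equal SDs, two-sided alpha 0.05, and detectable effects sized per day; 1.4.9 confirms neither the SDs nor the day. If the effect is the same on both days, pooling costs nothing and may gain power (80% to 98%). The weakness lies in the days differing, which the protocol's own rationale anticipates. The data needed for the right contrasts are already collected.

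**What to change.** In 9.9.2 and the synopsis:

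1. State that time indexes day and hour, or that each day is fitted separately.
2. Replace the single contrast by two prespecified ones per NeuroCart parameter: clonazepam minus placebo over the Day 1 post-dose times (1, 3, 5 h), and clonazepam minus placebo over the Day 22 times. Report each with estimate, 95% confidence interval and p-value, and keep the pooled effect as descriptive.
3. Define the baseline covariate as that period's Day 1 -1 h value. Call the Day 22 -1 h value an on-treatment measurement and state whether it counts in the Day 22 contrast.

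No added random term is needed. Treatment by time already allows the day contrasts, and a subject by treatment by day term would ask much of about 16 completers.

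The cost is wording, with no new visits, data or patients. The downside is two unadjusted contrasts per endpoint instead of one, in an analysis already declared exploratory and unadjusted (9.9.3).
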